### *Study Condition*

*Usual Care.* All participants will be in active OMAT at one of the two clinics. The current standard of care is to administer the state mandates Infectious Disease Behavioral screen. If women screen at risk for HIV, they are referred to the Colorado department of Public Health and Environment or Denver Public Health for further evaluation and follow up. At this time, neither program has standard work in place to assess pregnancy desire, contraception use and/or to provide information on contraception methods or referral to services. Standard care varies depending on the length of time a patient has been in treatment, but all are connected to a counselor and a treatment provider. The intention of this study is not to impact the care provided in OMAT, but to support reproductive behaviors and connection to a family planning visit.

*Peer-Led Reproductive Health Intervention.* After randomization, if the participant is assigned to the study intervention condition the researcher will introduce them to the peer navigator (PN) immediately after the baseline interview. The timing of each session is listed in the table below followed by a short summary of core objectives of each session. The PN intervention is specified in the Peer Navigator Handbook included with this submission.

Intervention Components		
Session	Timing	Duration
Session I	Immediately post-baseline	15 minutes
Session II	2-4 weeks post-baseline	20 minutes

Session One: The PN will conduct session one as outlined in the Peer Navigator Handbook. Core objectives of this session include engaging the patient in the intervention, assessing pregnancy intentions and current behaviors, advising patients on birth control options and summarizing the session and preparing for next steps. Motivational interviewing techniques will be used throughout the sessions. The primary goal of the first session will be to assess interest and readiness to connect to a family planning provider and to schedule a same day appointment for those patients who are ready to take action. It is estimated to take approximately 15 minutes.

- **If the participant is interested** in connecting to a family planning visit: The PN will make an appointment with an identified health educator (HE). A HE is a Denver Health employee who specializes in family planning education. All attempts will be made to make the appointment on the same day as session one.

- **If the participant is not interested** in connecting to a family planning visit: The PN will use the Topics (aka bubble sheet) and Values Worksheet (included in this submission) to determine if there are other areas or issues that the participant would like to discuss. If the participant is interested in being connected to a general practitioner, the PN will work to schedule an intake appointment from a list of identified DH providers who are experienced and interested in working with women in recovery. The PN will also have additional referral resources to provide the participant if there are other needs and/or concerns (outlined in the Peer Navigator Handbook).
- **Session Two:** The PN will attempt to conduct session two in person; however, participants will have the option of conducting session two over the phone. This session is expected to take approximately 20 minutes. The core content of this session will vary based on the results of the first session. If needed, motivational interviewing techniques will be used to continue to elicit self-change talk and increase motivation for a family planning provider visit. For participants who had a family planning visit, the PN will discuss any side effects or concerns the participant has with their birth control method. If the participant did not attend the appointment, the PN will facilitate the scheduling of a new appointment.

#### **D. Description, Risks and Justification of Procedures and Data Collection**

##### **Tools:**

Risks consist of potential embarrassment or discomfort in responding to sensitive questions. Participants may feel discomfort or embarrassment responding to questions about sensitive topics such as their knowledge and attitudes about reproductive health, STIs, pregnancy, and contraception. We believe this risk is low. Participants can choose not to respond to questions they are uncomfortable with. Additionally, if they are upset by the survey or have additional health related questions, we will refer them to a clinician on site (either behavioral health consultant or primary care provider/nurse). We will also provide an informational brochure at the end of the interview or focus group. The brochure will outline contraceptive methods and clinic locations.

There is a risk of loss of confidentiality but we believe this risk is low. All study data will be collected in a confidential setting and will be associated with a study ID and not with identifying information. Confidentiality cannot be assured in the focus groups participants will be informed of this risk.

As part of the study, we will collect a urine sample to test for pregnancy at baseline. If the participant received a positive pregnancy screening, they will be referred to the appropriate clinic staff, and excluded from participating in the study.

##### **E. Potential Scientific Problems:**

In the qualitative formative work, we will use purposeful sampling, which will not be representative of all women in OMAT. However, these data will be used to inform the development of an intervention that will be tested in a second phase (to be submitted once finalized).

Participants may not represent all women in treatment in Denver. We will make every attempt to understand and correct any recruiting biases, and recruit and enroll all eligible women receiving treatment at ARTS or OBHS during the time of the study.

Retention of participants for the second session, and for the three and six month follow-up interview is the biggest potential scientific problem. We intend to ask all participants for relevant contact information so that we can find them for their follow-up session and interviews.

These data are self-reported, which comes with limitations. However, several mechanisms are being put in place to reduce this bias, including: conducting the interview in a confidential setting; ensuring data is stored in a secure location; and using software so that participants can directly enter their answers into the computer. Literacy levels may also be a concern, but we will use survey software that will allow participants to hear and see the questions simultaneously. Additionally, a researcher will be available during the interview to address any comprehension concerns.

#### **F. Data Analysis Plan:**

*Phase I Qualitative Data Analysis.* All qualitative data will be digitally recorded and in written notes. The tapes from the individual interviews will be transcribed (and translated when necessary), verbatim, directly after the interview. Coding will begin immediately and will be ongoing so that subsequent interviews can be used to clarify emerging themes.

Individual interviews that have been transcribed will be imported into ATLAS.ti for coding. A grounded theory approach will be used to inductively code and analyze the individual transcripts. Coding for the first 3 interviews will take place as a team (the PI and research assistant). The team will immerse themselves in these interviews starting with reading each interview transcription several times to begin to identify meaningful themes. The team will code the three interviews, labeling as many concepts as emerge, and meet to jointly develop and operationalize codes that will be used in coding subsequent interviews. The team will code the remaining interviews, meeting weekly to discuss problems or questions with current codes and make modifications as needed. Analysis will be an ongoing iterative process. Relevant themes/categories and topics will be extracted for use in the development of the intervention and focus group interview guide.

The intent of the focus groups is to provide feedback on the intervention developed. Therefore, the focus groups will be digitally recorded and reviewed after the group meeting. Notes from these groups will be summarized and the intervention will be modified based on the findings. Following completion of the analysis and intervention development, the recordings will be destroyed.

*Phase II Quantitative Data Analysis.* Multivariate regressions will be performed to assess statistical differences between the intervention group and usual care group from baseline to follow-up with respect to:

**Hypothesis 1.** Participants randomized to the intervention will be more likely to follow-up with a family planning clinic visit.

- Participants with a family planning visit will show an increase in knowledge, self-efficacy, and perceived benefit of birth control.

**Hypothesis 2.** Participants randomized to the intervention will be more likely to initiate Long Acting Reversible Contraceptive (LARCS) methods.

Prior to conducting the primary analyses, group differences in baseline measures will be evaluated to ensure that the group assignment was even. We will also inspect the

distributions of continuous variables (e.g., frequency condom use) for departures from normality. Variables that exhibit non-normal distributions will be subjected to normalizing transformations prior to analysis. If those transformations are unsuccessful, analysis will proceed using non-parametric tools. In addition, the rate of attrition between baseline and follow-up interviews will be evaluated to ensure that it is relatively constant across intervention conditions, and that there are no systematic differences in the variables of interest between participants who completed the study and those lost to follow-up. Missing data due to item non-response or loss to follow-up will be handled using the most appropriate method, depending on the amount of missing data, the assumptions of the missing data (completely at random, at random or non-ignorable) and the assumptions of the method of handling missing data. For example, for small amounts of missing data that are assumed to be missing at random, listwise or pairwise deletion (the default in most statistical packages) will be sufficient. Variables that differ significantly between those who returned for follow-up and those who did not can also be controlled for in regression analyses. Where appropriate, we will use statistical models that employ maximum likelihood techniques of parameter estimation, allowing us to use participants with incomplete data and avoid the potential bias caused by listwise deletion. These techniques are robust under conditions of missing at random so comparisons of groups will not be biased as long as missing data is ignorable. The number of planned comparisons will be limited based on a priori hypotheses, therefore the per comparison error rate of .05 will be used to evaluate significance of the specific aims. Exploratory or secondary analyses will be adjusted for multiple comparisons using the Bonferroni test.

Many of the variables will be either summary index scores or latent variables that assess the psychological, behavioral and biological constructs of interest. For example knowledge will be a summary score representing the number of variables the participant correctly endorsed, while motivation will be a mean score across multiple variables representing the underlying latent construct. The variable related to use of LARCs will be a dichotomous variable representing current use or no current use of a LARC method (IUD or Implanon), as will attending a family planning visit during the study period.

Separate analyses will be conducted for each of the hypothesis to understand differential change over time. This includes looking at change scores as well as analysis of variance. The expectations for hypotheses 1 and 2 are that they will significantly increase in the intervention group. Differences will be assessed from baseline to follow-up period for each analysis.

Additional regression analyses will be conducted to identify significant predictors of differential change over time in birth control method and family planning visit. This analysis will determine if the intervention condition is a significant predictor of change. The regressions will account for any important statistically significant differences between groups at baseline. These differences may include variables pertaining to demographics, psychosocial factors, and behavioral variables. Generalized estimated equations (GEE) will be used to account for the within-subject correlation of repeated measures by individual patients. Group designations for the outcome analyses will adhere to the intention to treat threshold. All Statistical analyses will be performed using SAS (version 9.1 or later, SAS Institute Inc, Cary, NC) software.

*Engagement variables.* We will collect and analyze engagement with the PN and attendance to each session. These analyses will be used to assess intervention fidelity and to describe the amount of intervention each participant received to understand acceptability of the intervention as well as the relationship of intervention dose to study outcomes. These data will include, intervention activities covered and descriptive information such as the number of sessions attended, and the number of interactions with

the PN.

We will also record intervention sessions with the PN to determine the fidelity in which each session has been administered.

**Study Statistical Power.** Power analyses were done to assess the minimum detectable improvement needed for LARC uptake. A sample of 75 per group, using ITT approaches and assuming outcome if failure (dichotomous only) for patients who do not respond to follow-up surveys will provide 80% power to detect 23% difference between usual care and intervention patients on dichotomous outcomes, assuming an average success rate of 50% for maximum variability. For continuous outcomes, a follow-up sample size of 60 per group will provide 80% power to detect a .55 SD difference between usual care and intervention patients, or a medium linear effect over time (correlational structure CS with  $\rho=.5$ ).

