### **G. Summarize Knowledge to be Gained:**

This study will provide innovative information on the reproductive issues relevant to women in OMAT. It will use qualitative methods to develop a reproductive health intervention that can be delivered within the context of treatment. It will also provide information on the feasibility of this type of intervention. A randomized control trial in the second phase will provide important efficacy information on the impact of the intervention on participants' knowledge, family planning visits, and LARC uptake.

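### The sub-hypothesis on knowledge, self-efficacy and perceived benefit is written for women who had a family planning visit, so tested as worded it is not a randomised comparison

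*Combined protocol and SAP*

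**What the plan says.** Section IV.F (Data Analysis Plan) opens Phase II with a comparison of arms: "Multivariate regressions will be performed to assess statistical differences between the intervention group and usual care group from baseline to follow-up with respect to" the hypotheses that follow. Hypotheses 1 and 2 are both about women randomised to the intervention. The item indented under Hypothesis 1 changes the subject: "Participants with a family planning visit will show an increase in knowledge, self-efficacy, and perceived benefit of birth control". Section I gives Hypotheses 1 and 2 without this item, so Section IV.F is the only place that defines it.

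Later in Section IV.F the plan says of its separate analyses for each hypothesis: "This includes looking at change scores as well as analysis of variance". It adds "The expectations for hypotheses 1 and 2 are that they will significantly increase in the intervention group" and "Group designations for the outcome analyses will adhere to the intention to treat threshold". The further regressions are described for two outcomes only: "Additional regression analyses will be conducted to identify significant predictors of differential change over time in birth control method and family planning visit". The power paragraph sets continuous outcomes as usual care against intervention, without naming the outcomes. Section IV.G says the trial will show the impact of the intervention on "knowledge, family planning visits, and LARC uptake". It does not mention self-efficacy or perceived benefit.

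**The concern.** A family planning visit happens after randomisation, and the woman decides whether to go. It is also what Hypothesis 1 expects the intervention to change. The sentence can be read literally in three ways: before-after change in visitors, visitors against non-visitors, or the arms compared among visitors. None of them compares randomised groups.

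The protocol itself ties visiting to motivation. In Session One the peer navigator gauges each woman's interest and readiness, and offers a same-day appointment to those ready to act. A gain among visitors could therefore reflect who chose to go, repeat exposure to the survey, the peer sessions, or the visit, and the sentence as worded cannot tell these apart.

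Session One also covers birth control options before any visit takes place. If that advice raises knowledge in women who never attend, the sub-hypothesis misses it. What is at stake is a valid answer on knowledge, self-efficacy and perceived benefit.

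**Working it through.** **1. Text.** The Phase II lead-in, the intention-to-treat sentence and the continuous-outcome power statement all imply a comparison by arm. No sentence names the three scales in such a comparison. No sentence describes a visitor model, a comparator for visitors, or an adjustment for self-selection.

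**2. The plan's own power figures.** Two-sided .05 is assumed, because sidedness is not stated.
- Dichotomous: a 23-point difference centred on 50% is 38.5% v 61.5%. With 75 per arm, power is 81.1%, in line with the stated 80%.
- Continuous: 0.55 SD with 60 per arm gives noncentrality 0.55 × √(60/2) = 3.01 and power 84.8% (noncentral t, 118 df). The stated 80% is conservative, and this does not bear on the present point.

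**3. Assumed visit rates.** The documents give none.
- Scenario A borrows the power paragraph's placeholder rates and counts non-responders as failures ("assuming outcome if failure (dichotomous only) for patients who do not respond to follow-up surveys"). Visitors number 0.615 × 75 = 46.1 and 0.385 × 75 = 28.9. Among 60 followed up per arm that is 76.9% and 48.1%, or 62.5% overall.
- Scenario B assumes 30% v 10% of 75, which is 22.5 and 7.5 women. Among 60 per arm that is 37.5% and 12.5%, or 25% overall.

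Both scenarios place every visitor among the followed-up women.

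**4. Selection model (assumed).** Motivation M is standard normal. The log-odds of a visit are a + bM, with a set in each arm to match the visit rate. Score change is sM plus noise with total SD 1. There is no arm effect, no visit effect and no retest gain. Let m₁ and m₀ be mean M among visitors in the intervention and usual care arms, V the pooled visitor mean, q the overall visitor share, and N = -Vq/(1-q) the non-visitor mean. The spurious results are:
- before-after change in visitors: sV
- visitors minus non-visitors: s(V - N)
- arms among visitors: s(m₁ - m₀)

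Worked case, scenario A with b = 1.2 and s = 0.5: m₁ = 0.225, m₀ = 0.484, V = 0.325, N = -0.325 × 0.625/0.375 = -0.541. The results are 0.5 × 0.325 = 0.162, 0.5 × (0.325 + 0.541) = 0.433, and 0.5 × (0.225 - 0.484) = -0.129.

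| Scenario | b | s | Before-after, visitors | Visitors minus non-visitors | Arms among visitors |
|---|---|---|---|---|---|
| A or B | 0 | any | 0 | 0 | 0 |
| A | 0.8 | 0.3 | 0.073 | 0.194 | -0.059 |
| B | 0.8 | 0.3 | 0.148 | 0.197 | -0.063 |
| A | 1.2 | 0.5 | 0.162 | 0.433 | -0.129 |
| B | 1.2 | 0.5 | 0.333 | 0.444 | -0.155 |

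Under this model the comparison by randomised arm has expected difference zero in every row. The arms-among-visitors contrast is biased against the intervention, because usual care visitors are the more strongly selected group.

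**5. Power of the comparison by arm.** For 0.55 SD and 60 per arm, power is 84.8% at .05 and 72.0% at .05/3 = .0167. With the baseline score as covariate at the plan's correlation of .5, residual variance is 1 - 0.25 = 0.75, the effective difference is 0.55/√0.75 = 0.635 SD, and power is 93.2% and 85.1%.

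**The case against.** The strongest reply is that the sentence completes a lead-in that already compares the arms, and that intention to treat and the power statement point the same way. On that view the wording is loose and no non-randomised analysis has been specified. Much of this stands: the plan nowhere sets out a visitor model. But adding the lead-in to a sentence about visitors gives at best arms compared among visitors, which is still not a randomised comparison.

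A second reply is that this is a deliberate question about mechanism. Visits go through a health educator who specialises in family planning, self-efficacy and perceived benefits are constructs of the Health Belief Model, and Aim 3 plans exploratory work on that model. That is plausible and is a reason to keep the question. It is not a reason to leave it unlabelled under an efficacy hypothesis with no analysis of its own.

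Third, the figures rest on assumptions. That is right. The plan's 50% is chosen for maximum variability and is not a visit rate. Visits may also be taken from clinical records, so some survey non-responders could be known visitors.

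A reader might infer that the trial's main efficacy conclusions are compromised, or that a grossly inflated false-positive rate has been shown. The documents support neither. Visiting and starting a long-acting method are both stated by randomised group, and nothing in the documents fixes how strongly visitors select themselves.

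**Conclusion.** The concern holds for this one sentence. As worded, the sub-hypothesis describes a self-selected group formed after randomisation, and no other text states a comparison by arm for the three scales. A result obtained that way would not be the intervention effect on knowledge announced in Section IV.G.

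Size is illustration only. Across the two assumed visit-rate scenarios, mid-range selection gives spurious results of about 0.07 to 0.15 SD (before-after), 0.19 to 0.20 SD (visitors against non-visitors) and -0.06 SD (arms among visitors). The strongest assumed selection gives up to about 0.33, 0.44 and -0.16 SD. Without selection all three are zero. The conflict in wording does not depend on these inputs. This should be corrected before analysis, but it is not a flaw in the main comparisons.

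**What to change.** Replace the item under Hypothesis 1 with: *Women randomized to the intervention will show a greater increase in knowledge, self-efficacy and perceived benefit of birth control than women randomized to usual care.* Analyse it by randomised group regardless of visit, with the baseline score taken into account, using the repeated-measures and missing-data methods already in Section IV.F. If the link between visiting and these scales is of interest as mechanism, keep it as an exploratory, non-randomised association and label it so.

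Two details can be settled in the same edit. Say whether the .05 per-comparison rule or the Bonferroni rule applies to the three scales, and name the survey scale meant by perceived benefit, a term the Phase II survey list does not use.

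The cost is one or two sentences, with no new participants, visits or methods. There are two downsides. A visit-based result would lose confirmatory status. If the three scales are treated as secondary under Bonferroni, power for 0.55 SD with 60 per group is about 72% instead of 85%, or about 85% instead of 93% with baseline adjustment. That loss comes from the multiplicity rule and not from the rewording.

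### For continuous scores and 30-day counts, inspection of the data chooses between raw, transformed and unnamed non-parametric analysis, so the effect measure is not fixed in advance and the precision of baseline adjustment may be lost

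*Combined protocol and SAP*

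**What the plan says.** The rule is in the combined protocol and SAP, section F (Data Analysis Plan), Phase II. Continuous variables are to be inspected for departures from normality; the example given is frequency of condom use. Then: "Variables that exhibit non-normal distributions will be subjected to normalizing transformations prior to analysis". And: "If those transformations are unsuccessful, analysis will proceed using non-parametric tools". No test or threshold defines non-normal or unsuccessful, no transformation is named, and the non-parametric method is not identified.

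The variables concerned are bounded scores and counts. In section F, "knowledge will be a summary score representing the number of variables the participant correctly endorsed", and motivation is a mean over items. The Phase II survey content in section IV lists 30-day counts of sex acts, contraceptive use and condom use. LARC use and attendance at a family planning visit are defined as dichotomous, so the rule does not reach them.

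Other parts of section F bear on the same outcomes. It opens Phase II with regressions from baseline to follow-up. It mentions change scores and analysis of variance, and likelihood methods for incomplete data where appropriate. Under Study Statistical Power, "a follow-up sample size of 60 per group" is said to be enough: it "will provide 80% power to detect a .55 SD difference between usual care and intervention patients", or a medium linear effect over time under compound symmetry with a correlation of .5. The error rate for the specific aims is "the per comparison error rate of .05"; secondary and exploratory analyses get a Bonferroni adjustment.

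**The concern.** A raw-scale model estimates a difference in means. A transformed analysis estimates a difference or ratio on another scale. A rank test addresses the tendency of one group to score higher. These are different quantities, and the plan lets the look of the data decide which one is reported. Two analysts could follow the text faithfully and report different effects, and a rank result cannot be read against the planned 0.55 SD.

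The second issue is precision. The text does not say whether the fallback uses the baseline value, both follow-ups or participants with incomplete data. Section E names retention as the biggest potential scientific problem, so silence on incomplete cases matters. If the fallback is a simple two-group rank test at one visit, information already collected is discarded.

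The affected outcomes are supporting ones, but they are not trivial. Knowledge, self-efficacy and perceived benefit are listed under Hypothesis 1, Aim 3 concerns Health Belief Model constructs, and section G names knowledge among the results expected from the trial.

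**Working it through.** **Inputs from Study Statistical Power:** 60 per group, 0.55 SD, 80% power, compound symmetry with ρ = .5. Alpha is .05 per comparison; sidedness is not stated, so two-sided is assumed.

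**1. The plan's own figure.** n per group = 2(1.960 + 0.842)² / 0.55² = 51.9, so 52 (53 by t-test), not 60. At 60 per group, 0.55/√(2/60) = 3.0125 and power = Φ(3.0125 − 1.960) = 85.4% (84.8% by t-test). The difference detectable with 80% power is 2.802 × √(2/60) = 0.51 SD. The stated figure is conservative and does not reproduce exactly.

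**2. Unadjusted rank test, one follow-up.** Multiply 3.0125 by the square root of the relative efficiency.
- Normal data (0.955): Φ(2.944 − 1.960) = 83.7%.
- Minimum efficiency (0.864): Φ(2.800 − 1.960) = 80.0%.

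**3. Baseline-adjusted regression (ANCOVA).**
- One follow-up, variance factor 1 − 0.5² = 0.75: Φ(3.0125/√0.75 − 1.960) = 93.6%; detectable difference 0.44 SD.
- Mean of both follow-ups, factor (1 + 0.5)/2 − 0.5² = 0.5: Φ(3.0125/√0.5 − 1.960) = 98.9%; detectable difference 0.36 SD.

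**4. Simulation.** 60 per arm, ρ = .5, 4,000 replicates, Monte Carlo SE at most 0.8 points. The documents give no distributions, so all shapes are assumptions. The score has latent mean 8 and SD 2, rounded and limited to 0–10, with a 0.55 SD latent shift. The count is negative binomial with mean 5, size 0.5 and log mean ratio 0.8. The lognormal has a 0.55 shift on the log scale. Power (%) at one follow-up:

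| Shape | t-test | Rank-sum | Rank-sum on change | ANCOVA | Rank ANCOVA |
|---|---|---|---|---|---|
| Normal | 84.5 | 83.1 | 82.6 | 93.1 | 91.3 |
| Ceiling-limited score | 80.2 | 80.5 | 72.6 | 88.8 | 88.3 |
| Overdispersed count | 80.1 | 62.9 | 73.6 | 87.2 | 73.3 |
| Lognormal, untransformed | 67.0 | 83.9 | 82.6 | 73.4 | 91.5 |

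Type I error, checked for the normal and count shapes, was 4.5 to 5.8%. A separate run for a ceiling-limited score gave 82% for the rank-sum test. Formula and simulation together therefore put the unadjusted rank test at about 81 to 84% and ANCOVA at about 89 to 94% for normal and ceiling-limited data. With both follow-ups averaged, unadjusted rank against ANCOVA is 92 v 99% (normal) and 90 v 97% (score).

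**5. Where the gap comes from.** For scores, compare like with like in the table. Without baseline, t-test and rank-sum differ by 1.4 points (normal) and −0.3 points (score). With baseline, ANCOVA and rank ANCOVA differ by 1.8 and 0.5 points. Adding baseline is worth about 8 to 9 points on either scale. A second check (ceiling-limited score, 0.45 SD, correlation 0.6) agrees: ANCOVA 81%, rank ANCOVA 79 to 80%, unequal-variance t-test 64%, rank-sum 63 to 64%.

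**6. Not computed.** None of these runs simulates the full inspect, transform, fall-back sequence or missing data. The harm from the data-driven choice itself is argued, not measured.

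**The case against.** Several stronger readings are tempting, and the documents do not support them.

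- **Non-parametric methods cannot handle baseline or covariates.** The plan never says rank tests, and rank ANCOVA carries both. The gap is in specification, not capability.
- **The rule as such costs power.** For scores, ranking costs under 2 points like for like. For skewed variables the direction depends on the shape: the rank-sum test loses to raw-scale ANCOVA for the assumed count (63 v 87%) and beats it for the lognormal (84 v 73%).
- **The fallback contradicts promised methods.** The GEE and covariate sentences sit in a paragraph on birth control method and family planning visit, and likelihood methods are promised only where appropriate. The planned parametric route for scores may itself use change scores without baseline adjustment, in which case falling back to ranks would lose little.
- **Planned power is breached.** Not at alpha .05 for a rank test at follow-up on near-normal or ceiling-limited scores. A rank test on change for a ceiling-limited score did fall to 73 to 76%, but a t-test on change was also below 80%, at 78%. If three scores formed a Bonferroni family (an assumption; alpha .0167), power would be 66 to 71% for an unadjusted rank test and 86% for ANCOVA. An unadjusted mean comparison would also fall, to Φ(3.0125 − 2.394) = 73%.
- **Sixty per group was chosen to allow for a rank test.** 52/0.864 = 60.2 fits, but the documents give no such reasoning.
- **The fallback will nearly always be triggered.** The plan says only to inspect, and gives no item counts, means or zero fractions, so the frequency is unknown.

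What stands is the missing criterion, the unnamed method and the silence on baseline, repeats and incomplete cases.

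**Conclusion.** The point holds for continuous scores and 30-day counts only. Section F leaves the effect measure to be settled after the data are inspected, with no criterion and no named fallback. If the fallback is an unadjusted rank test at one follow-up, it forgoes roughly 8 to 10 points of power at the plan's own inputs for normal or ceiling-limited scores. That is precision given up by omitting baseline; it does not take power below the stated 80% at alpha .05. For counts, the size and direction depend on a distribution that the documents do not give.

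The result rests on two-sided alpha, the plan's ρ of .5, assumed shapes and complete follow-up of 60 per arm. A reader might infer that the trial's main comparisons are at risk. They are not: the LARC and family planning visit outcomes are binary and never enter this rule. The change is still worth making, because it fixes the estimand at almost no cost.

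**What to change.** In section F, delete the inspect, transform, then non-parametric sequence and state in advance:

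- **Index and mean scores:** a repeated-measures model on the original scale using the 3- and 6-month values, adjusted for the baseline value of the outcome, with robust (sandwich) standard errors.
- **30-day counts:** a log-link model, for example negative binomial, with the baseline count as a covariate.
- **Sensitivity only:** a rank-based analysis, preferably baseline-adjusted.

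Distributions can still be described, but should not select the analysis. The cost is SAP wording and one additional count model; no extra participants or data are needed.
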